## **Study background and purposes:**

Patellar tendinopathy (PT) is an overuse condition characterized by repetitive stress on the patellar tendon, leading to structural changes in the tendon due to accumulated microtrauma. It is prevalent among athletes involved in sports requiring extensive jumping, such as volleyball and basketball, with a higher incidence in males than females. More than one-third of athletes may not return to their previous level of activity within six months of treatment, and severe cases may even necessitate the cessation of their athletic careers. Previous research has found that patients with PT symptoms for more than three months tend to reduce the use of the knee joint for energy absorption during landing. While this mechanism may prevent further deterioration of the injured patellar tendon, it redistributes energy loading to other joints during landing, increasing the energy absorption required at the hip joint and potentially leading to other lower limb injuries in the long term. This highlights the importance of the hip joint in addition to the knee joint for such athletes. However, previous studies have mainly focused on changes in landing patterns in the sagittal plane in athletes with patellar tendinopathy, lacking research on the other two planes and muscle activation during landing. Changes in landing patterns can be observed not only biomechanically but also through movement control. Alterations in movement patterns are also associated with muscle activation and movement control.

Similar investigations have been conducted for other knee conditions such as anterior cruciate ligament injuries and patellofemoral pain syndrome, but there is currently no research specifically addressing symptomatic athletes with patellar tendinopathy.

Understanding the muscle activation and biomechanical changes during landing in athletes with patellar tendinopathy can help identify potential issues in clinical practice and implement exercise adjustments to prevent secondary problems and exacerbation of symptoms, while normalizing movement patterns in athletes.

Additionally, the hip joint plays a crucial role in closed kinetic chain movements. If the relationship between joint movement control issues and patellar tendinopathy can be identified, it could serve as a simple assessment tool in clinical practice to determine the risk of developing patellar tendinopathy.

In summary, patellar tendinopathy may be associated with changes in landing patterns. However, the biomechanical alterations of the hip and knee joints in the frontal and transverse planes are still unclear. Furthermore, factors affecting movement patterns, such as movement control and muscle activation status, remain to be elucidated. Therefore, the purpose of this study is to investigate movement control in athletes with patellar tendinopathy and the biomechanical characteristics of the hip and knee joints during landing tasks. We hypothesize that athletes with PT symptoms will demonstrate poorer movement control abilities compared to those without

symptoms, and during the landing phase of loaded movements, they will exhibit increased hip adduction, greater hip extension torque, higher quadriceps activation, delayed gluteal activation timing, and earlier rectus femoris activation timing.

## **Study design and participants:**

This is a cross-sectional observational study. Participants aged 18 to 40 were recruited for the experiment. The symptomatic group was selected based on the following criteria, and then matched to find an asymptomatic group.

Inclusion criteria for the symptomatic group were:

- ✓ Experiencing anterior knee pain during loading activities for more than three months
- ✓ Pain localized only to the inferior pole of the patella
- ✓ Having participated in collegiate-level or higher volleyball/basketball-related sports training for at least two years
- ✓ Currently engaging in activities inducing knee pain for at least 90 minutes per week
- ✓ Scoring below 80 on the Chinese version of the Victorian Institute of Sport Assessment-patellar tendinopathy questionnaire (VISA-PCh).

Inclusion criteria for the asymptomatic group were:

- ✓ Having participated in collegiate-level or higher volleyball/basketball-related sports training for at least two years
- ✓ Currently engaging in related activities for more than 90 minutes per week
- ✓ Reporting no lower limb pain scores greater than 3 (on a scale of 10) in the past three months
- ✓ Scoring greater than or equal to 80 on the VISA-PCh questionnaire.

Any of the following conditions in either the symptomatic or asymptomatic group led to exclusion from recruitment:

- ✓ Undergoing relevant rehabilitation exercises for knee pain in the past three months
- ✓ Having other chronic lower limb pain issues
- ✓ Self-reporting pregnancy
- ✓ History of lower limb surgery or patellar tendon steroid injections
- ✓ Medical history of rheumatic, immune, or neurological systemic diseases.

## **Study methods:**

Data on participants' gender, age, height, weight, exercise frequency and duration, years of sports experience, specific sports discipline, participation in highest-level competitions, history of lower limb injuries, and completion of the

Chinese version of the Victorian Institute of Sport Assessment-patellar tendinopathy

questionnaire were collected via cloud-based forms. Using this information, eligible

participants were screened, with the symptomatic group recruited first. Then,

individuals in the asymptomatic group were matched to the symptomatic group based

on gender, age ( $\pm 10\%$ ), height ( $\pm 10\%$ ), weight ( $\pm 10\%$ ), and sports discipline.

Before testing, researchers conducted a second screening to confirm eligibility. If eligible, researchers provided detailed explanations of the study procedures and purposes to participants, who then signed informed consent forms. Prior to testing, participants warmed up for 5 minutes. Testing was conducted in the following order:

Jump height testing: Participants wore athletic shoes and performed a vertical jump test, followed by stationary and spike jump tests. Each test was performed three times for practice and three times for formal testing. The average of the formal test results, minus the average fingertip reach height, yielded the jump height results.

Ankle dorsiflexion angle measurement: Participants stood facing a wall with hands on the wall for support. While maintaining a lunge position with the front heel on the ground, participants dorsiflexed the ankle to its maximum angle. The angle formed between a line segment from the tip of the fibula to 10 cm below the lateral malleolus and the horizontal line was measured. The angle measurement was performed three times for each foot, and the average was taken.

Motor control testing: four tests were performed to assess hip and knee joint control, including hip flexion control, internal rotation control, external rotation/abduction control, and hip adduction control. Each test was practiced three times and performed formally five times.

Loading testing: Participants performed countermovement jump, drop vertical jump, and step-down test to assess lower limb function. Each test was performed according to specific protocols.

Muscle electromyography (EMG) data collection: EMG electrodes were placed on both gluteus maximus, biceps femoris, rectus femoris, vastus lateralis ,and participants performed maximal voluntary isometric contractions. Additionally, handheld dynamometry was used to measure hip extensor strength.

Finally, data processing and statistical analysis were performed to complete the experiment.

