## **Data analysis:**

The total scores of motor control tests of the symptomatic group's pain foot were summed and converted into percentages, which were then compared with the average total scores of the control group's bilateral foot tests to assess lower limb control ability between the two groups.

Reflective ball trajectories were captured using a motion capture system equipped with eight high-speed cameras, sample rate at a frequency of 100 Hz. Force data were collected using two force plates measuring 60 cm in length and 40 cm in width, sample rate at a frequency of 1000 Hz. The data were integrated via analog/digital conversion boards and analyzed using Nexus 1.8.1 motion analysis software. The plug-in gait model was employed to calculate raw data, yielding three-dimensional angles and moments of the hip and knee joints, as well as maximum ground reaction forces.

Surface electromyography (EMG) data were obtained at a sampling frequency of 1500 Hz. MATLAB programming was utilized to filter and rectify signals within the 20-450 Hz range, with root mean square calculated at 20-millisecond intervals and signal windows set at 1 millisecond to reduce signal data alterations. Muscle activation during movements was standardized using maximum voluntary contractions, computing the average and maximum activation of muscles during movements. Muscle activation onset was defined as the baseline value plus three standard deviations above the mean of the pre-movement period, with the time point indicating the onset of muscle activation identified accordingly.

For all variables except muscle activation onset time, data points within  $\pm 0.01$  seconds of the required data were averaged to obtain the final results, thereby

minimizing the impact of extreme values.

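### Were the EMG electrodes really applied after the movements whose muscle activity is analysed?

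*Combined protocol and SAP*

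**What the plan says.** Study methods introduces the session with "Testing was conducted in the following order". Four labelled items follow: jump height, ankle dorsiflexion, motor control and loading. For the last it says "Participants performed countermovement jump, drop vertical jump, and step-down test to assess lower limb function", and adds that each test followed its own protocol, which is not reproduced.

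The next paragraph, in the same labelled style, covers EMG: "EMG electrodes were placed on both gluteus maximus, biceps femoris, rectus femoris" and vastus lateralis, and "participants performed maximal voluntary isometric contractions". Hip extensor dynamometry is mentioned there too. The section then closes by turning to data processing and statistics.

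Data analysis describes how the EMG signals are used: "Muscle activation during movements was standardized using maximum voluntary contractions", "computing the average and maximum activation of muscles during movements". Onset is set by a threshold of "three standard deviations above the mean of the pre-movement period". Study background and purposes places the EMG hypotheses (quadriceps activation, gluteal timing, rectus femoris timing) in landing under load.

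On recruitment, Study methods says "with the symptomatic group recruited first", with controls then matched to the cases.

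**The concern.** Read as a timeline, the section applies electrodes only after every movement task is over. Such a session could yield no EMG from landing, yet three of the six hypotheses depend on it.

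The second worry is the denominator. Quadriceps activation is expressed relative to each participant's maximal contraction, and the text does not settle whether that contraction came before or after the jumps and landings. A maximum taken after hard exertion, in people selected for knee pain on loading, might be lower and would inflate the normalised value. Because cases were recruited before controls, one could also ask whether procedure drifted between the groups. If it did, the unadjusted t-test would mix procedure with muscle activation.

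**Working it through.** The plan gives no figure to reproduce. The check compares the sections and adds a little algebra.

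**1. Is the literal order possible?** No. Both the activation measures and the onset threshold in Data analysis need a signal recorded in the movement trial, the latter including a stretch before movement starts. Every movement task is listed before the EMG paragraph and none after it. Electrodes must therefore have been on earlier than the list implies.

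**2. Is the list a full timeline?** Probably not. Data analysis relies on reflective markers and force plates, yet Study methods never says when markers were applied. The list covers tests and leaves out set-up. The EMG paragraph is labelled as data collection, and the closing sentence has left the test session for the study as a whole. On this reading the announced order ends with the loading tests, and the EMG paragraph describes a measurement made alongside them.

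**3. Which hypotheses depend on the timing of the maximal contraction?** The six are movement control, hip adduction, hip extension torque, quadriceps activation, gluteal onset and rectus femoris onset.
- Using EMG: 3 of 6.
- Using the maximal contraction as denominator: 1 of 6 (quadriceps activation).
- The two onset hypotheses use a pre-movement baseline. They need only that electrodes were on.

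**4. What would a late maximal contraction do?** Suppose, as an assumption outside the documents, that prior effort lowers every participant's maximal EMG by a fraction x. Each normalised value is then multiplied by 1/(1 − x):
- x = 5%: 1/0.95 = 1.05
- x = 10%: 1/0.90 = 1.11
- x = 20%: 1/0.80 = 1.25

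Both group means, both standard deviations and hence the standard error are multiplied by the same factor. It cancels in t = (difference in means)/(standard error), so the t statistic and p-value do not move.

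**5. When would it not cancel?** When the reduction differs by group. With equal true landing activity, the case-to-control ratio is (1 − control reduction)/(1 − case reduction). For an assumed 10% in cases only it is 1/0.90 = 1.11; for 10% in controls only it is 0.90. These figures describe any group difference in the maximum, whatever its cause. They do not measure an effect of test order, and the documents give neither size nor direction.

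**6. Is there evidence of different orders by group?** No. One sequence is described for all participants. The statement about recruiting cases first belongs to screening and matching.

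**The case for a change.** The strongest case for acting is that the text does announce an order, gives no sign that the order stops before the EMG paragraph, and ends as though a sequence has been completed. A reader can infer that electrodes went on early, but cannot infer when the maximal contractions were done, because both possibilities fit Data analysis. Study methods lists six jumps per jump test (three practice, three formal), so 12 to 18 jumps depending on whether two or three tests are meant, and then the loading tests. In athletes with load-related knee pain, that is a relevant detail of an outcome defined as a ratio, and supplying it takes a sentence or two.

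Much of this stands. The order as printed cannot be literal, the timing of the maximal contractions is unstated, and a methods report should give it. But the request is only to record what was done. It calls for no reordering, new data or new analysis. Pain-limited effort in cases could affect the maximum under either order, so stating the order would not remove that possibility. The suggestion that order differed between groups has no support in the text.

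**Conclusion.** No change to the plan is needed. The contradiction is genuine on a strict reading, but it is best explained as a fault in how the methods were laid out: a competent team records movement EMG with the electrodes already on. The real gap is the timing of the maximal contractions, which bears on one of six hypotheses. The documents show no effect on that one; a common proportional reduction leaves its t-test exactly as it was.

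This rests on two assumptions: that the EMG paragraph describes a measurement and not a fifth step, and that the single sequence described applied to both groups. The text supports both, though it states neither outright. Session records showing that the order differed between cases and controls would reopen the question for quadriceps activation. Otherwise the order is a detail for the study report.

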## **Data analysis:**

The total scores of motor control tests of the symptomatic group's pain foot were summed and converted into percentages, which were then compared with the average total scores of the control group's bilateral foot tests to assess lower limb control ability between the two groups.

Reflective ball trajectories were captured using a motion capture system equipped with eight high-speed cameras, sample rate at a frequency of 100 Hz. Force data were collected using two force plates measuring 60 cm in length and 40 cm in width, sample rate at a frequency of 1000 Hz. The data were integrated via analog/digital conversion boards and analyzed using Nexus 1.8.1 motion analysis software. The plug-in gait model was employed to calculate raw data, yielding three-dimensional angles and moments of the hip and knee joints, as well as maximum ground reaction forces.

Surface electromyography (EMG) data were obtained at a sampling frequency of 1500 Hz. MATLAB programming was utilized to filter and rectify signals within the 20-450 Hz range, with root mean square calculated at 20-millisecond intervals and signal windows set at 1 millisecond to reduce signal data alterations. Muscle activation during movements was standardized using maximum voluntary contractions, computing the average and maximum activation of muscles during movements. Muscle activation onset was defined as the baseline value plus three standard deviations above the mean of the pre-movement period, with the time point indicating the onset of muscle activation identified accordingly.

For all variables except muscle activation onset time, data points within  $\pm 0.01$  seconds of the required data were averaged to obtain the final results, thereby

minimizing the impact of extreme values.

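### EMG onset is a mean + 3 SD threshold with no minimum time above it; if the first crossing was taken, resting noise can be recorded as onset and weaken the two timing comparisons

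*Combined protocol and SAP*

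**What the plan says.** The combined protocol and SAP treats onset in its Data analysis section. The sampling rate is given: "Surface electromyography (EMG) data were obtained at a sampling frequency of 1500 Hz". The smoothing is described as "with root mean square calculated at 20-millisecond intervals and signal windows set at 1 millisecond to reduce signal data alterations". The threshold is "Muscle activation onset was defined as the baseline value plus three standard deviations above the mean of the pre-movement period", and the time is then taken from it: "with the time point indicating the onset of muscle activation identified accordingly". The section gives no minimum time above threshold, baseline length, search window or visual check. It gives no time zero either, although Study methods lists three loading tasks (two jumps and a step-down).

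The next paragraph averages values over ±0.01 s, but "For all variables except muscle activation onset time"; its stated aim is "minimizing the impact of extreme values".

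Onset time matters because the Study background and purposes section predicts "delayed gluteal activation timing, and earlier rectus femoris activation timing" in symptomatic athletes, "during the landing phase of loaded movements". These are two of six stated hypotheses. The Statistical analysis section compares muscle activities between groups with independent-samples t-tests.

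**The concern.** A threshold alone does not define an onset. Resting EMG is noise, and a smoothed noise signal will now and then exceed its own mean by three SDs. If the first such moment is taken as onset, some recordings get an onset that precedes the true one. A crossing that must last for a minimum time excludes nearly all of these, and the text asks for none.

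Two wordings make the rule harder to reproduce. The threshold sentence names a baseline level and also a pre-movement mean, so the baseline could be counted once (mean + 3 SD) or twice (2 × mean + 3 SD). The RMS sentence, taken literally, computes an RMS from one or two samples every 20 ms.

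At stake is the power of the two timing comparisons. If early false onsets are equally likely in both groups, they dilute a real difference and add scatter. They do not create a difference.

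**Working it through.** The plan states no sample size, effect size, SD of onset time or power, so there is no figure of its own to reproduce.

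**From the documents.** 1500 Hz sampling, 20-450 Hz band, mean + 3 SD, 20 ms and 1 ms RMS values, t-test at 0.05.

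**Assumed.** Two-sided test; baseline 0.5-1.0 s; 0.1 or 0.3 s of rest searched before true onset; 20 per group; 3 trials averaged; between-person SD 30-80 ms; standardised difference 0.909, which gives 80% power with error-free onsets.

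**Samples per window.**
- 1500 × 0.001 = 1.5
- 1500 × 0.020 = 30
- 1500 × 0.025 = 37.5, so 38

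An RMS over 1.5 samples smooths almost nothing. A 20 ms window moved in 1 ms steps is the likely intent.

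**Simulation.** White noise was band-passed at 20-450 Hz, with 9,000 rest recordings per baseline length. Recorded onset = min(true onset, first false crossing). Each power setting used 4,000-12,000 simulated studies.

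| Rule | False onsets, 0.1 s / 0.3 s | Power, 0.1 s / 0.3 s |
|---|---|---|
| 20 ms sliding window, first crossing | 6-8% / 17-21% | 73-78% / 25-60% |
| Literal 1 ms every 20 ms, first crossing | 5-7% / 15-18% | 71-77% / 26-62% |
| Non-overlapping 20 ms blocks, first crossing | 2% / 5-7% | 78-80% / 51-73% |
| 20 ms sliding window, 25 ms hold | at most 0.16% | 76-81% |
| 2 × mean + 3 SD, 20 ms window, first crossing | 0% | 78-81% |

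The last two rows cover every search length tried, up to 1.0 s. A second simulation with separate code gave 7-9% / 17-22% (sliding) and 6-7% / 15-17% (literal). Together, the sliding and literal readings give 5-9% and 15-22%.

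**Why the difference shrinks.** A false onset replaces the true one, so the expected group difference is roughly (1 − p) × the true difference, where p is the false-onset rate. At 0.5 s baseline and 0.3 s search:
- sliding: 1 − 0.208 = 0.79 (simulated 0.78)
- literal: 1 − 0.181 = 0.82 (simulated 0.80)
- blocks: 1 − 0.074 = 0.93 (simulated 0.92)

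Added scatter accounts for the rest of the loss. In the same setting with SD 50 ms, power with 1 / 3 / 5 trials averaged is 24 / 41 / 51% for the sliding window, and 80% throughout with a 25 ms hold.

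**Different assumptions.** This run used 200 ms baseline, 200 ms search, a 50 ms activation ramp, SD 30 ms and a 20 ms sliding window. Power was 0.28 (one trial) and 0.49 (three trials) with a first crossing, against 0.78 and 0.79 with a 25 ms hold. Type I error was 0.050; in the main simulation it was 4-6%.

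**A real 1 ms window.** In the same 200/200 ms setting, with three trials and a hold of two points (40 ms), power was 0.61, 0.71 and 0.76 for SD 20, 30 and 50 ms. A hold does not fully repair a signal sampled once every 20 ms.

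**The case against.** The strongest reply is that this is a gap in reporting and not a demonstrated error. The text never says that a bare first crossing was used, and the MATLAB code may contain a hold or a visual check. That stands, and it is why every power figure here is conditional. The range is also wide. With 0.1 s of rest searched the loss is at most 9 points (80 − 71), and the block reading loses less again.

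Four stronger readings are tempting, and the documents do not support them.
- *The study's onset times are wrong.* The documents do not show which rule the script applied. With the baseline counted twice and a 20 ms window, false onsets vanish and power is 78-81%. If the speed of activation varies between people, that version gives 62-78% against 71-80% with a hold, a smaller and more speculative gap.
- *The swapped RMS values cause the damage.* Under a first crossing, the sliding and literal readings give nearly the same power. The swap is mainly an error of wording, unless the 1 ms window was really used.
- *Onset was denied a protection against extreme values.* The ±0.01 s averaging smooths signal values around an instant. Onset is itself an instant, so leaving it out is natural and no fault.
- *Power is nearly all lost.* That appears only with 1.0 s of rest searched (5-11% for the sliding and literal readings), which is an upper bound not shown to fit a landing task.

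It is also fair to say that any non-significant t-test is weak evidence of no difference. What remains is that the rule, followed as naturally read, measures two stated hypotheses less well than a simple alternative would.

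**Conclusion.** The point holds in conditional form; its severity is minor to moderate. As written, onset is a crossing of the pre-movement mean + 3 SD with no required duration, on an RMS signal whose printed window is too short to be meaningful. If the first crossing was taken with the baseline counted once, about 5-9% of recordings (0.1 s searched) to 15-22% (0.3 s searched) would carry a false early onset. Power would then fall from an assumed 80% to about 71-78% or 25-62% respectively.

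The sizes rest on assumed baseline and search lengths, trial count, SD and group size. Group size hardly matters to the relative loss: with the difference reset to 80% power, 12, 20 and 40 per group give 39, 43 and 42% for the sliding window. The conclusion also assumes false onsets equally likely in both groups; unequal resting activity could add bias, which was not simulated. Under the equal-error assumption a positive timing result is not called into question, but a null one would be harder to interpret.

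**What to change.** First read the existing MATLAB script and report:
- the threshold formula
- RMS window and step
- baseline period and search window
- time zero for each loading task
- number of trials averaged
- any hold or visual check

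The rule to state is as follows. RMS uses a 20 ms window (30 samples) moved in steps of about 1 ms. The threshold is the pre-movement mean + 3 SD, with the baseline counted once. Onset is the first sample after which RMS stays above threshold for a time fixed in advance and longer than the RMS window. One large noise value stays in a sliding window for up to 20 ms, so a shorter hold would not exclude it. A hold of 25 ms (38 samples) is an example and not a value from the documents; 30 and 50 ms serve as sensitivity checks. With a 0.2 s baseline and 1.0 s search, a harsh setting, holds of 25 / 30 / 50 ms leave 1.2 / 0.6 / 0.03% false onsets.

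Reprocess the stored EMG, blind to group, only if the script took a bare first crossing of mean + 3 SD or really used a 1 ms window. Otherwise change only the text, so that it describes what was run, including a double-baseline threshold if that was used.

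The cost is a look at the script and one paragraph of text; at most, also a few lines of code and a short rerun. No new data are needed. The downside is that genuine bursts shorter than the hold are not counted as onset.
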